This study aims to examine the effect of an educational program on improving the mental health literacy of general hospital nurses, in terms of knowledge of mental health, mental illnesses, and their treatment; attitude or stigma about mental illnesses; and help-seeking efficacy. It also measures the interventional effect on perceived competency in caring for patients with mental illness and work stress among general hospital nurses, as well as patient satisfaction with nursing care in general hospitals.

Study design

This study is a prospective 2-arm parallel controlled trial. Randomized controlled trials

were not feasible for this study because of the risk of contamination (Kahan et al., 2016). It would be difficult to “blind” healthcare professionals to their assigned group because they could easily disseminate information within and between units during clinical sharing or conversation at the common facilities of the same hospital, such as changing rooms and canteen. Two study hospitals will be assigned to the intervention arm or control arm by tossing a coin.

Study setting

The study sites will be conducted in the emergency departments and medical wards of two regional general hospitals. It was because patients with physical-mental comorbidity were mostly caring in this area (Weichert, 2019; Woon & Redzuan, 2019). The two hospitals are similar in nature and the service provided. Both study hospitals provide a comprehensive range of acute, rehabilitation, and ambulatory service for the people living in the western part of the New Territories of Hong Kong. (Pok Oi Hospital, 2022; Tuen Mun Hospital, 2022). These two hospitals had two emergency departments and 18 medical wards, serving about 270,000 patients annually and at least hundreds of nurses were working collaboratively with doctors and allied health in these units (Pok Oi Hospital, 2022; Tuen Mun Hospital, 2022). Indeed, psychiatric consultation-liaison services had been provided in both hospitals since the 1990s.

Eligibility criteria

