The inclusion criteria of the participants will be full-time registered nurses (general) or enrolled nurses (general) who care for adult patients in emergency departments or medical wards. There is no restriction on participants' socio-demographic characteristics, such as gender and age. The exclusion criteria are a nurse who had a professional registration in the psychiatric stream, who does not understand Chinese and English, or who is unable to access or use the internet.

Sample size

According to the systematic review of the effectiveness of interventions in improving the mental health literacy of healthcare professionals in general hospitals, the effect size of an effective intervention ranged from Cohen's $d = 0.75$ to 1.32 . However, the outcomes concern only a particular component of mental health literacy. Therefore, a more conservative effect size, Cohen's $d = 0.5$ was used for estimation of the sample size of the current study. It is estimated using GPower that a sample size of 64 participants per group is adequate to detect an effect size of 0.5 on the primary outcomes at a post-intervention time point with 80% power at a 5% level of significance. Assuming an attrition rate of 15% (Catalogue of Bias Collaboration et al., 2017), this study will recruit 150 nurses (75 per group).

Recruitment

The sampling method will be convenience sampling. Recruitment of participants will be solicited via a public announcement by the poster and electronic mail. The potential subjects will be screened based on the inclusion and exclusion criteria. An information sheet will be sent via electronic mail to the eligible nurses to provide information about the study including its purpose, data collection procedures, etc. In addition, voluntary participation and the right to withdraw from the study freely at any time without any consequences will also be reinforced. Moreover, all participants will be informed that a monetary incentive, a cash coupon of HKD 50, would be given upon completion of all the measurements to compensate for the time spent. Written informed consent will be obtained from the participants before the study's commencement.

Study intervention

The intervention group will receive an educational program consisting of six 30-minutes online educational sessions and followed by one 60-minutes face-to-face session (Refer to Table 1.).

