In the first part, the six online educational sessions will be delivered on a private YouTube channel which consists of information about mental health literacy (knowledge about mental health, mental illnesses, and their management, attitude/ stigma related to mental illnesses, and

help-seeking efficacy), pre-post session questionnaires, and an online discussion forum. After educational materials were validated by two experienced psychiatrists and two advanced practice psychiatric nurses, educational videos will be uploaded to the private YouTube Channel and allowed participants to have six weeks of unrestricted access. Interactions will be facilitated through an online discussion forum and relevant articles, or web pages will be posted to facilitate further learning. The attendance of participants will be tracked and those who had trouble accessing the content will be contacted by the research team proactively. To reduce attrition, the research team will contact participants weekly, and maintain ongoing communication through email. A friendly email reminder will be sent to participants who fail to complete access all the educational videos 5 days before the free access period ends. 80% attendance will be considered to be good compliance. After 6-weeks of free access to online education, participants will be arranged into small groups for a 60-minute face-to-face session.

The second part is a face-to-face session which consists of problem-based learning and group sharing. In problem-based learning, participants will be divided into a group of 7-8 people. This session will be conducted by the associate consultant of the psychiatric consultation-liaison service and facilitated by the researcher. Participants were invited to read the vignettes of a patient with a mental illness in a general hospital. Two vignettes were provided, which are based

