on the clinical scenarios which can happen in participants' work and are meant to illustrate patients with physical-mental comorbidity in a general hospital who might benefit from psychiatric consultation-liaison service. Through group discussion, participants had to come up with the diagnosis of the case and offer an opinion on action that can be taken by general hospital nurses in helping patients with mental illnesses in general hospitals. In the group sharing, a summary of information about general hospital nurses' mental health literacy obtained in the online education will be presented. Participants can identify the common mental health knowledge deficit, mental illness-related beliefs, and barriers in help-seeking among general hospital nurses who care for patients with mental illnesses. Participants are encouraged to share their personal experiences related to mental health literacy and to explore strategies for dealing with difficulties of caring for patients with mental illnesses in general hospitals, such as how to manage their own emotions when confronted with a challenging scenario. Furthermore, discussions will be guided on further strategies for promoting mental health literacy of healthcare professionals in general hospitals. For this session, the mode of delivery will be changed into zoom meetings according to the situation of disease outbreaks. The total duration of the educational program is 4 hours, and the intervention period will be seven weeks.

The control group will not receive any educational intervention related to mental health

literacy.

Data collection

Before starting the educational program, the socio-demographic data of the participants including age, gender, marital status, education level, occupation, and working years will be collected. The information from participants will be collected through the self-reported form. The collection of these data can provide a more comprehensive picture of the background of the participants and allow initial equivalence among the study groups to be examined.

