Hospital Patient Satisfaction Survey (Huang & Yen, 2015) will be used to assess patient satisfaction with nursing care in general hospitals. There are eight questions on the scale to measure patient satisfaction with nursing care during the hospitalization with a 4-point Likert scale (from "0"=never to "4"=always). The scale had a good psychometric property with a content validity index of .97, item discrimination critical ratio of 28.61 to 50.25, and item correlations ranged from .68 to .84. The exploratory factor analysis with item factor loadings (factors of "professional knowledge and skill" and "environmental control") ranged from .61 to .84, explaining 71.40% of the total variance. The internal consistency was Cronbach's

alpha= .97. (Huang & Yen, 2015).

Data analysis

Statistical analyses

Statistical Package for Social Science will be used for data analysis will be employed for all statistical analyses.

Descriptive statistics were used including means, standard deviations, medians, quartiles, and ranges for age, years of working years, and relative frequencies for gender, marital status, highest education, and occupation. Independent t, Mann-Whitney, chi-square, or Fisher's exact tests, as appropriate, to compare the socio-demographic characteristics between groups. For the outcomes, the generalized estimation equations (GEE) model will be used to examine the intervention effects. Each of the outcomes will be compared between groups with adjustment for potential confounding factors, for example, characteristics of participants shown statistically different between arms at baseline. An intention-to-treat, repeated measures analysis will be conducted to compare changes in the two groups over time. Three effects will be evaluated including the time effect, group effect, and time x group interaction effect. A 2-sided p value less than .05 will be considered statistically significance for all analyses.

Timetable of work

[figure not shown]

Figure 1. Timetable of work

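### The 80% power and the 5% level rest on an unstated assumption of independent nurses, and with one hospital per arm any hospital-specific change cannot be separated from the programme effect.

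*Combined protocol and SAP*

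**What the plan says.** All references are to the combined protocol and SAP.

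- **Sample size.** With Cohen's d = 0.5, "a sample size of 64 participants per group is adequate to detect an effect size of 0.5 on the primary outcomes". The claim is for 80% power at the 5% level, and for a single assessment after the intervention. The software is named (GPower) but the test is not. There is no ICC, design effect, baseline-post correlation or statement that nurses are treated as independent.
- **Study design.** "Two study hospitals will be assigned to the intervention arm or control arm by tossing a coin".
- **Study setting.** "The two hospitals are similar in nature and the service provided". Also: "These two hospitals had two emergency departments and 18 medical wards". The split of these 20 units between the hospitals is not given.
- **Study intervention.** For the face-to-face part, "participants will be divided into a group of 7-8 people". This applies to the intervention arm only.
- **Data collection.** At baseline "age, gender, marital status, education level, occupation, and working years will be collected". Ward or department is not named.
- **Statistical analyses.** "the generalized estimation equations (GEE) model will be used to examine the intervention effects". The section plans an intention-to-treat, repeated-measures comparison of change in the two groups, and also a between-group comparison of each outcome adjusted for confounders. Time, group and time x group effects are all to be evaluated, at two-sided .05. It does not say which effect is primary, what the GEE cluster is, or which variance estimator is used.

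**The concern.** Nurses on the same ward share patients, managers and conversation. The Study design section itself argues that information passes easily within and between units of a hospital. If scores, or changes in scores, are correlated within unit, a GEE that clusters only on nurse gives intervals that are too narrow, and its nominal 5% test rejects too often.

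The hospital level is a separate matter. With one hospital per arm, anything that changes in one hospital and not the other during the study appears in the same contrast as the programme. Followed as written, the plan could report such a change at p < .05 as an effect of the education.

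**Working it through.** **Inputs from the plan:** d = 0.5; 64 evaluable nurses per group; two-sided 5%; one hospital per arm; 20 units in total; test-retest correlation .797 for the primary scale (Measurements, primary outcome).

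**Inputs assumed, because the plan gives none:** every ICC, the hospital autocorrelation, the baseline-post correlation other than .797, and an even split of 10 units per arm.

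**1. The plan's own figure.** Two-sample t-test, noncentrality = d × √(n/2) = 0.5 × √32 = 2.83, df = 126. Power is 80.1% at 64 per group and 79.5% at 63. So 64 is correct for independent nurses at one time point, without baseline. The t-test is inferred from this match.

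**2. Ignored unit correlation, no hospital effect.** With 10 units per arm, m = 64/10 = 6.4 nurses per unit.
- Design effect: DE = 1 + (m − 1) × ICC = 1 + 5.4 × ICC.
- Type I error of the uncorrected test: 2 × [1 − Φ(1.96/√DE)].
- Power for a single post score: noncentral t with effective n = 64/DE, using 126 df (design effect alone) or 2 × 10 − 2 = 18 df (unit-level test).

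| Unit ICC | DE | Effective n per arm | Type I error if ignored | Power, 126 df | Power, 18 df |
|---|---|---|---|---|---|
| 0 | 1.000 | 64.0 | 5.0% | 80% | 76% |
| 0.01 | 1.054 | 60.7 | 5.6% | 78% | 74% |
| 0.05 | 1.270 | 50.4 | 8.2% | 70% | 66% |
| 0.10 | 1.540 | 41.6 | 11.4% | 62% | 58% |

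About 4 points of the gap between the last two columns are loss of degrees of freedom, not clustering. The ICC is that of the quantity tested: scores for a group effect, change for time x group.

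**3. What baseline does to power (no clustering, 126 df).** For a change score the standardised effect is 0.5/√(2(1 − r)). At r = 0.3, 0.5 and .797 it is 0.423, 0.500 and 0.785, giving power of 66%, 80% and 99%. With baseline as a covariate the effect is 0.5/√(1 − r²). At r = 0.5 it is 0.577, giving 90%.

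Clustering and baseline combined, for change with 18 df and unit ICC 0.05: 52%, 66% and 96% at r = 0.3, 0.5 and .797. Power can therefore end up on either side of 80%.

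**4. Hospital level, if the two hospitals are viewed as random draws (hospital ICC 0.01).**
- Group effect at one time point: DE = 1 + 63 × 0.01 = 1.63, so type I error is 12.5%.
- Time x group: with hospital autocorrelation c and nurse correlation r, ICC_change = ICC(1 − c)/[ICC(1 − c) + (1 − ICC)(1 − r)] and DE = 1 + 63 × ICC_change.

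| c | r = 0.5 | r = .797 |
|---|---|---|
| 1 (stable differences) | 5.0% | 5.0% |
| 0.9 | 6.5% | 8.7% |
| 0.8 | 8.0% | 12.4% |

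Stable hospital differences cancel in time x group, but hospital-specific change does not. Two hospitals in two arms leave 2 − 2 = 0 degrees of freedom to estimate it.

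**The case against.** The strongest reply is that the 80% ignores baseline, while the plan measures baseline and analyses repeated measures, so actual power may be well above 80%. That stands. A reader might infer that the trial is underpowered, or that 64 is a miscalculation. The documents support neither: the arithmetic is right, and step 3 shows power moving in both directions with a correlation the plan does not give. The plan also calls d = 0.5 conservative against reported effects of 0.75 to 1.32. That margin helps power, but it does nothing for the type I error or for confounding.

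Second, time x group removes stable hospital differences, and the comparison of change in Statistical analyses points that way. This is right as far as it goes. The section also lists a group effect and a between-group comparison, so the test is not settled, and hospital-specific change remains in either case.

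Third, the hospital error rates treat hospitals as random. If inference is conditional on these two hospitals, a hospital-specific change is a fixed bias and those rates do not apply. This is also right, so step 4 is illustration and not an estimate of this trial's error rate.

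Fourth, the hospitals are described as similar and confounders are adjusted for. Both may reduce the problem. Neither replicates hospitals within an arm, and the characteristics to be collected describe nurses, not events in a hospital. The use of one hospital per arm is disclosed, but its consequence for inference is not.

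**Conclusion.** The point holds as an unstated assumption plus an unacknowledged confounding. The 80% and the 5% level require no within-unit and no hospital-specific correlation in the quantity tested. The plan neither says so nor names a cluster level or primary effect that would deal with it. Under an assumed unit ICC of 0.01 to 0.10 and 10 units per arm, the uncorrected test has a type I error of 5.6 to 11.4%. A reduction in power is possible but not shown.

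Hospital-specific change is inseparable from the programme whatever the ICC. A reader might infer that clustering the GEE on hospital would cure this. It would not, because there would be two clusters, one per arm, and no usable robust variance for the group contrast. This should be fixed before baseline data are collected, since unit membership is not among the listed fields.

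**What to change.** 1. **Sample size.** State that 80% assumes independent nurses and a post-intervention score without baseline. Add power for the named primary contrast over a short range of unit ICC (for example 0 to 0.10) and baseline-post correlation, showing the loss from degrees of freedom separately.
2. **Data collection and Statistical analyses.** Record a coded unit (ward or emergency department) at baseline. Name one primary effect; time x group at the immediate post-intervention assessment fits the planned comparison of change. Analyse nurses nested in unit, either by GEE clustered on unit with small-sample-corrected variance, or by a mixed model with unit and unit-by-time random effects and small-sample degrees of freedom. A unit intercept alone would cancel in the change contrast.
3. **Interpretation.** State that inference is conditional on these two hospitals, and that unit clustering does not address hospital-specific change or the face-to-face groups. Limit the conclusion to a difference in change between the two hospitals.

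**Cost:** revised wording and one added field, which should be coded because unit together with age, gender and occupation could identify a nurse. Intervals will usually be somewhat wider and the stated power may look less favourable. No extra recruitment is needed.

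### Intervention nurses are taught in groups of 7-8, but neither the sample size nor the GEE allows for correlation within those session groups

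*Combined protocol and SAP*

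**What the plan says.** Under Study intervention, after six weeks of online access, "participants will be arranged into small groups for a 60-minute face-to-face session", and "In problem-based learning, participants will be divided into a group of 7-8 people". The same section says of the other arm: "The control group will not receive any educational intervention related to mental health". The timetable places the first follow-up assessment straight after programme completion, and so after the group session.

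Under Sample size: "It is estimated using GPower that a sample size of 64 participants per group is adequate to detect an effect size of 0.5". That figure refers to the primary outcome at the first follow-up after the programme, and it is set "with 80% power at a 5% level of significance". The section adds "Assuming an attrition rate of 15" per cent and recruits 75 per group. It mentions no ICC or design effect.

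Under Statistical analyses: "the generalized estimation equations (GEE) model will be used to examine the intervention effects", as an intention-to-treat repeated-measures analysis with time, group and time-by-group effects. Group there means trial arm. No cluster unit, working correlation, variance estimator or session-group term is named. The test level is given by "A 2-sided p value less than .05 will be considered statistically significance for all analyses".

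**The concern.** Nurses who work through cases and share experiences in one small group may come out more alike than nurses from different groups. The protocol's learning theory relies on this: participants are meant to learn by watching and responding to one another. Any such similarity adds variance between session groups in the intervention arm and none in the control arm. A GEE clustered on the nurse accounts for the repeated scores of one person, not for correlation between people in the same session. The protocol does not tie session groups to wards, so a ward term would not reliably pick this up.

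At stake are the width of the confidence interval for the programme effect, the false-positive rate of its test, and the meaning of the 80% power figure. If session membership is not recorded when the sessions run, it may not be recoverable later.

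**Working it through.** **Inputs.** From the documents: group size 7-8 (m = 7.5 used), intervention arm only; 64 analysed per arm; d = 0.5, so SD = 1; two-sided 5%; 15% attrition; test-retest correlation of the primary scale 0.797 (Measurements). Assumed: ICC 0.01 to 0.10, with total variance held at 1 and no hospital or ward effect.

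**Step 1: reproduce the plan.** A two-sample noncentral t calculation with d = 0.5 and two-sided 5% needs 64 per arm and gives 80.1% power. One-sided versions give 50 or 51 and do not match. Attrition leaves 75 × 0.85 = 63.75, with 80.0% power. The match needs a design effect of 1, and there is no slack after attrition.

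**Step 2: number of groups.** 75/7.5 = 10 groups recruited; 64/7.5 ≈ 8.5 groups analysed.

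**Step 3: effect of grouping in one arm.**
- Intervention-arm design effect: DE = 1 + (7.5 − 1) × ICC.
- The variance of the difference is multiplied by (1 + DE)/2, and the SE by its square root.
- Error of a test that ignores grouping: 2 × [1 − Φ(1.96/SE ratio)].
- Power: noncentral t with SE = √(DE/64 + 1/64) and 126 df. The last column uses Satterthwaite-type df based on about 8.5 groups.

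Example at ICC 0.05: DE = 1 + 6.5 × 0.05 = 1.325; (1 + 1.325)/2 = 1.1625; SE ratio = 1.078; 1.96/1.078 = 1.818; error 6.9%.

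| ICC | DE | SE ratio | Error if ignored | Power, 126 df | Power, small-sample df |
|---|---|---|---|---|---|
| 0.01 | 1.065 | 1.016 | 5.4% | 78.9% | 76% |
| 0.02 | 1.130 | 1.032 | 5.8% | 77.6% | 75% |
| 0.05 | 1.325 | 1.078 | 6.9% | 74.0% | 71% |
| 0.10 | 1.650 | 1.151 | 8.9% | 68.4% | 64% |

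Using m = 7 or 8 moves power at ICC 0.05 only to 74.5% or 73.5%.

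**Step 4: an analysis that uses baseline.** For change from baseline with baseline-post correlation r, the control variance is 2(1 − r). The intervention arm has 2(1 − r) + 6.5 × ICC, because the group effect enters at the post visit only. By normal approximation, power = Φ(0.5/SE − 1.96).
- At r = 0.797 and ICC 0.05, the variances are 0.406 and 0.731. SE = √(1.137/64) = 0.133 and power is 96%. At ICC 0.10 it is 91%.
- Power reaches 80% when 4(1 − r) + 6.5 × ICC ≤ 64 × (0.5/2.80)² ≈ 2.04. That means r of at least about 0.57 at ICC 0.05 and 0.65 at ICC 0.10.
- At r = 0.797 and ICC 0.05, the SE ratio is √(1.137/0.812) = 1.183, so the error of a test that ignores grouping is about 10%. A high correlation protects power but makes the relative understatement of the SE larger.

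**The case against.** The strongest reply is that the size rests wholly on an ICC with no source in the documents, and that there are reasons to expect a low one. The session is one hour of four. The same consultant role leads it and the researcher facilitates. Nothing suggests that the two vignettes, or the summary presented, differ between groups. Content common to all groups shifts the whole arm and creates no variance between groups; only group-specific discussion and composition do. This stands. At ICC 0.01 the loss is about one point of power, which is negligible.

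Three stronger readings are tempting and are not supported:
- A reader might infer that the plan declares the nurses independent. It does not. It is silent on the cluster unit, and clustering on the nurse is only the natural reading of a repeated-measures GEE.
- A reader might infer that the trial is underpowered. Step 4 shows that an analysis using baseline could keep more than 80% power. The trial's own baseline-post correlation is unknown, and at r = 0.5 the losses of Step 3 return.
- A reader might take 5.4% to 8.9% as the trial's true error rate. With one hospital per arm, that range describes session grouping alone.

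That hospital confounding is the larger problem is also true. It lowers the priority of this point but does not remove it, since session grouping is a separate source that can be modelled.

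**Conclusion.** The point holds in conditional form and is minor. It is established that grouping occurs in one arm only, that the sample size assumes independence, and that the analysis section makes no stated provision for session groups. If the GEE clusters on the nurse, the standard error is too small for any positive session-group ICC, whether or not baseline is used.

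For the post-intervention comparison at 64 per group, an ICC of 0.01 to 0.10 gives the 2% to 15% SE shortfall and 5.4% to 8.9% error in the table. Power for the two-sample comparison on which the trial was sized falls to about 79% to 68%, or about 76% to 64% with small-sample degrees of freedom. These figures assume 7.5 per group, total variance fixed at 1, and no hospital or ward effect. The loss of power in the planned repeated-measures analysis is not shown.

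**What to change.** - Record the session group that each intervention nurse attends.
- State the GEE cluster unit, and allow for session-group correlation in the intervention arm at the two post-course visits. Treat control nurses, and intervention nurses who attend no session, as singletons. Either a partially nested mixed model or a GEE clustered on session group will serve, with a small-sample correction for the roughly 8 to 10 groups. Keep this in addition to any ward term.
- State that the 80% power assumes no session-group correlation, and give the range above.

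The cost is one variable, a few sentences in the plan and a slightly wider interval. If the sponsor wants 80% power for the two-sample comparison despite grouping, the same 126-df type of calculation needs 66, 68, 74 or 85 analysed per arm at ICC 0.01, 0.02, 0.05 or 0.10. Dividing by 0.85 and rounding up gives 78, 80, 88 or 100 recruited per arm. None of this resolves the separate confounding of hospital with treatment.

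### The nurse's unit (emergency department or medical ward) is not a listed baseline variable, so the planned equivalence check and GEE adjustment would miss a difference in unit mix between the two hospitals

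*Combined protocol and SAP*

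**What the plan says.** - **Who is eligible.** Under Eligibility criteria, participants are general-stream nurses "who care for adult patients in emergency departments or medical wards". The two settings are pooled.
- **Where they work.** Study setting states: "These two hospitals had two emergency departments and 18 medical wards". It gives no split by hospital and no nurse numbers per unit.
- **How they are recruited.** Recruitment states: "The sampling method will be convenience sampling". Volunteers respond to a poster or e-mail. No section sets a quota, stratum or matching by unit.
- **How arms are formed.** Study design states: "Two study hospitals will be assigned to the intervention arm or control arm by tossing a coin". Each arm is therefore one hospital.
- **What is recorded.** Data collection lists six items, "including age, gender, marital status, education level, occupation, and working years will be collected", and gives as one purpose to "allow initial equivalence among the study groups to be examined".
- **What is analysed.** Statistical analyses summarises age and working years, plus "relative frequencies for gender, marital status, highest education, and occupation". These are the same six items. The GEE comparison is made with "adjustment for potential confounding factors, for example, characteristics of participants shown statistically different between arms at baseline". Time, group and time x group effects are all evaluated, and none is named as the primary test.

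**The concern.** Individual nurses are not randomised, so the arms are comparable only as far as the two sets of volunteers are alike and measured differences can be adjusted for. Unit type is an obvious way in which they could differ. It defines eligibility, nothing in recruitment balances it, and a single coin toss between two hospitals cannot. Two of the nurse-reported outcomes, work stress and perceived competency (which includes resource issues), ask nurses about their own work and practice, so dependence on the unit is plausible.

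The plan's safeguards are a baseline comparison and covariate adjustment, and both can act only on recorded variables. If one arm drew mainly from its emergency department and the other mainly from its wards, the baseline table as listed could look balanced while the arms differed in setting. Some of the difference between settings could then be read as an effect of the programme.

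**Working it through.** **The plan's own figure.** Sample size takes d = 0.5, 80% power and a 5% level (two-sided, per Statistical analyses). An exact two-sample t calculation gives 80.1% power at 64 per group and 79.5% at 63, so 64 reproduces. For 15% attrition, 64/0.85 = 75.3, which rounds up to 76. The stated 75 leaves 75 x 0.85 = 63.75, a trivial shortfall. The point made here does not change the sample size.

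**How unit mix enters.** Let p_I and p_C be the shares of emergency nurses in the intervention and control arms. Let D(t) be the emergency-minus-ward difference in mean score at visit t, without any programme. If the programme does nothing and the hospitals differ only in unit mix:

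- difference between arms at visit t = (p_I - p_C) x D(t);
- time x group contrast, post v baseline = (p_I - p_C) x [D(post) - D(baseline)].

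If D is constant over time, the second expression is zero and the first is not. A standing level difference therefore cancels in time x group, but it remains in a group effect (taken at one visit or averaged over visits) and in a post-intervention comparison. Only a difference in *change* between units reaches time x group.

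**Inputs.** The documents give neither the shares nor D(t). All values of these below are assumptions.

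**Route 1: difference in change, read from time x group.** Bias = share difference x difference in change.

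| Share difference | Difference in change 0.3 SD | Difference in change 0.5 SD |
|---|---|---|
| 10 points | 0.10 x 0.3 = 0.03 SD | 0.10 x 0.5 = 0.05 SD |
| 30 points (e.g. 50% v 20%) | 0.30 x 0.3 = 0.09 SD | 0.30 x 0.5 = 0.15 SD |

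**Route 2: level difference, read from a post-intervention comparison.** Bias = share difference x level difference. The chance of p < .05 with no programme effect comes from the noncentral t at 64 per group.

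| Share difference | Level difference 0.2 SD: bias, false-positive rate | Level difference 0.5 SD: bias, false-positive rate |
|---|---|---|
| 10 points | 0.02 SD, 5.1% | 0.05 SD, 5.9% |
| 20 points | 0.04 SD, 5.6% | 0.10 SD, 8.7% |
| 40 points | 0.08 SD, 7.3% | 0.20 SD, 20.2% |

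The rates in Route 2 apply only to a post-intervention comparison. They must not be carried over to time x group, where a level difference cancels.

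**Are such share differences possible?** Suppose both hospitals had the same underlying emergency share p and 75 independent volunteers each. The difference in observed shares would then lie within 1.96 x sqrt(2p(1-p)/75) in 95% of cases: about 10 points at p = 0.1, 15 at p = 0.3 and 16 at p = 0.5. A gap near 10 points can thus arise by chance. A gap of 30 points would need a systematic difference between the hospitals in who volunteers, which convenience recruitment permits and the documents neither show nor exclude.

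**The case against.** The best reply is that the plan is less closed than it looks. The baseline list opens with the word including, so it need not be exhaustive. The adjustment rule gives baseline differences only as an example. Occupation is undefined. The unit must be seen at screening, and a linkage file between study code and identity is kept. This stands to the extent that a reader who infers that unit mix *cannot* be checked or adjusted for goes too far. The documents support only that the plan does not say it will be. Occupation may mean no more than registered or enrolled nurse, and the analysis section adds no unit variable.

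The second reply is that the outcomes are measured at baseline, so standing differences cancel. That is right for time x group. It does not cover the group effect, which is also tested, or the post-intervention contrast on which the trial is sized.

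Third, no passage says that emergency and ward nurses change differently over time. Study setting puts both together as the places where these patients are mostly cared for, and calls the hospitals similar. This stands as a limit on how likely the bias is. The similarity claimed is of institutions, however, not of the volunteers' unit mix. Two further inferences should be resisted:

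- **Seasonal workload.** A reader might suppose that winter pressure eases differently in the two settings during the study. The documents describe no such pattern. Recruitment starts in September 2022, baseline follows consent and the intervention starts at the end of February 2023, so the baseline month is not fixed.
- **Opportunity to use the teaching.** A reader might count this as a source of bias. It can act only in the arm that is taught. It would make the average effect depend on that arm's mix, which is effect modification; it would not make an ineffective programme look effective.

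Finally, arm is fully confounded with hospital whatever is done about unit. That is true, but unit mix is one part of the hospital difference that can be measured.

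**Conclusion.** The gap is real and inexpensive to close. Unit type is an eligibility criterion, is left unbalanced by recruitment and allocation, and is absent from both descriptions of the baseline data, so the equivalence check and adjustment as written would miss an imbalance in it.

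The size is unknown. Under the assumed 10 to 30 point share difference and 0.3 to 0.5 SD difference in change, the bias in time x group is 0.03 to 0.15 SD. The lower end is negligible. If unit mix is alike in the two hospitals, or the two settings change in parallel, the bias in time x group is zero.

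It is tempting to express 0.03 to 0.15 SD as 6% to 30% of the planned effect (0.03/0.5 and 0.15/0.5) and conclude that the primary result is threatened to that degree. The documents do not support this. The 0.5 was set for the primary outcomes, whereas the plausible case for drift by unit concerns work stress and perceived competency, which are secondary. Nothing in the documents indicates that mental health literacy drifts differently by unit in untaught nurses.

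**What to change.** - In Data collection, add current unit (emergency department or medical ward, and which ward) to the baseline data, carried over from eligibility screening.
- In Statistical analyses, tabulate unit by arm, and prespecify unit type and unit type x time in the GEE for the nurse outcomes whatever the baseline p value.

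The cost is one form item and three extra parameters per outcome over three visits (one for unit type, two for its interaction with time). A matched emergency-to-ward recruitment split in both hospitals is optional. It would help to ensure that both unit types are represented in both arms, but may slow recruitment; if so, keep the item and the adjustment without it.

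The report should still say that, with one hospital per arm, hospital and programme effects cannot be separated. Recording the unit removes one measurable part of that problem and leaves the rest.
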